7.1.2.1. Within Vaccine Group Analysis

Descriptive statistics will be compiled for Month 78 (Year 6) through Month 126 (Year 10) for each antibody obtained via rSBA and via hSBA. For each vaccine group, at each blood sampling time point, for each antigen assessed:

- GMTs with 95% CIs will be tabulated.
- Percentages of subjects with titers above the proposed cutoffs with exact 95% CIs will be calculated.
- The distribution of antibody titers will be tabulated and also presented using reverse cumulative distribution curves.

7.1.2.2. Between Vaccine Group Analysis

Exploratory comparisons of the differences between ACWY≥2 and MenPS will be compiled for Month 78 (Year 6) through Month 126 (Year 10) for each antibody obtained via rSBA and via hSBA. However, exploratory comparisons of the differences between ACWY<2 and MenCCRM will be compiled Month 78 (Year 6) through Month 126 (Year 10) only for MenC (via rSBA and via hSBA) because MenCCRM does not contain components for A, W-135, or Y.

MenACWY-TT-100 (C0921004)

Exploratory evaluations of the differences in the immune response will be performed in terms of:

- Differences in the percentage of subjects with rSBA titers ≥1:8 and ≥1:128 and hSBA titers ≥1:4 and ≥1:8 between the ACWY≥2 and MenPS (primed) groups, with their standardized asymptotic 95% CIs for the 4 serological groups.
- Differences in the percentage of subjects with rSBA-MenC titers ≥1:8 and ≥1:128 and hSBA-MenC titers ≥1:4 and ≥1:8 between the ACWY<2 and MenCCRM (primed) groups with their standardized asymptotic 95% CIs.
- Ratio of GMTs between the ACWY≥2 and MenPS vaccine groups for the 4 serological groups and the ratio of MenC GMTs between the ACWY<2 and MenCCRM (primed) vaccine groups, with their 95% CIs. Both rSBA and hSBA will be analyzed. This will be performed using an analysis of variance (ANOVA) model on the logarithm10 transformation of the titers using the vaccine group as covariate. In each pairwise comparison, the ANOVA model will use only data from the 2 groups being compared. The ANOVA for ratio of GMTs between the ACWY≥2 and MenPS groups will also include age strata 2-<6 and 6-<11 years of age at primary vaccination.

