1.2. Rationale for the study and study design

In study MenACWY-TT-027, 613 healthy subjects between 1 and 10 years of age were randomized using a (3:1) ratio to receive either a single dose of MenACWY-TT vaccine or a meningococcal C conjugate vaccine or a meningococcal polysaccharide vaccine. The subjects were followed up for antibody persistence over five years post-vaccination in studies MenACWY-TT-028 through -032. The results showed that subjects vaccinated with MenACWY-TT between ages 1 and 2 years of age had detectable antibodies five years after vaccination in 73.5%, 77.6%, 34.7% and 42.9% of subjects against serogroups A, C, W-135 and Y, respectively. Subjects vaccinated with MenACWY-TT at 2-10 years of age in this same study showed that five years after vaccination 90.8%, 90.8%, 78.6% and 78.6% of subjects had detectable antibodies against A, C, W-135 and Y serogroups, respectively. The main purpose of this study is to continue to evaluate the antibody persistence 6, 7, 8, 9 and 10 years post-administration of MenACWY-TT conjugate vaccine as compared to *Meningitec* or *Mencevax ACWY* when given to healthy subjects 1 to 10 years of age. In addition, the safety and immunogenicity of a booster dose of MenACWY-TT vaccine administered to all eligible subjects 10 years after the primary vaccination will be evaluated.

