10.5.1.2.2. Between group analysis

An exploratory evaluation of the differences in the immune response at approximately 78, 90, 102, 114 and 126 months after the primary vaccination will be performed in terms of:

- Differences in the percentage of subjects with rSBA titres ≥1:8 and ≥1:128 and hSBA titres ≥1:4 and ≥1:8 between the ACWY≥2 and MenPS (primed) groups, with their standardized asymptotic 95% CIs for the four serogroups and the differences in the percentage of subjects with rSBA-MenC titres ≥1:8 and ≥1:128 and hSBA-MenC titres ≥1:4 and ≥1:8 between the ACWY≤2 and MenCCRM (primed) groups with their standardized asymptotic 95% CIs.
- Ratio of GMTs between the ACWY≥2 and MenPS groups for the four serogroups and the ratio of MenC GMTs between the ACWY≤2 and MenCCRM (primed) groups, with their standardized asymptotic 95% CIs. This will be performed using an Analysis of Variance (ANOVA) model on the logarithm₁₀ transformation of the titres using the vaccine group and age stratum as covariates.

Modelling prediction

In order to complement the descriptive analyses of observed persistence per time point and minimize the bias that may have occurred due to the loss to follow-up after the vaccination, a longitudinal analysis will be performed at the last persistence time point before booster vaccination for rSBA-MenA, C, W-135 and Y and/or hSBA-MenA, C, W-135 and Y.

More details on the modeling predication that will be done will be further described in the Statistical Analysis Plan (SAP).

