7.1.3. Modeling Prediction

In order to complement the descriptive analyses of observed persistence per time point, longitudinal analyses will be performed at Month 126, which is the last persistence time point before booster vaccination.

Except as noted below, these longitudinal analyses will include all titers from:

- Pre- and post-primary analyses (Month 0 and Month 1 in Study MenACWY-TT-027) for subjects belonging in the ATP cohort for immunogenicity,
- Months 12, 24, 36, 48, and 60 (in Studies MenACWY-TT-028, 029, 030, 031, and 032 respectively) for subjects belonging in the ATP cohort for persistence in corresponding studies and
- Months 78, 90, 102, 114, and 126 (in Study MenACWY-TT-100) for subjects belonging in the ATP cohort for persistence at Month 78 up to Month 126, respectively.

Age group is nearly confounded with vaccine group. Subjects 1-<2 years are assigned only to ACWY<2 and MenCCRM vaccine groups, while subjects 2-<11 years are assigned only to ACWY>2 and MenPS vaccine groups. Therefore the longitudinal analyses will be performed separately in the 2 age strata.

MenACWY-TT-100 (C0921004)

Titers below the cutoff will be set at half the value of the cutoff. The time points will be considered as categorical. The model will be fitted via the proc mixed procedure according to the following code, depending on the age cohort:

```
* for 1-<2 year subjects;

*Model 1 – Repeated model on all available time points;

PROC MIXED data=sero;

CLASS group time;

MODEL log_val = group | time;

Repeated time / TYPE=UN SUBJECT=pid;

RUN;

*for 2-<11 year cohort;
```

PROC MIXED data=sero;

CLASS group time age cat;

MODEL log val = group | time age cat;

Repeated time / TYPE=UN SUBJECT=pid;

RUN;

where 'age cat' will be defined as '2-<6 yr' and '6-<11 yr'.

The exceptions and limitations to the longitudinal analyses are:

- rSBA titers at Year 4 will be limited to PHE titers, even though GSK also obtained some Year 4 titers, because PHE performed all subsequent rSBAs.
- Only MenC titers will be analyzed in the 1-<2 year age group because MenCCRM does not have an A, W-135, or Y component.
- hSBA analyses for the 2-<11 year age group will be limited to Month 78 (Year 6) through Month 126 (Year 10) time points because there are no hSBA titers for 2-<6 year subjects (see Table 5).

MenACWY-TT-100 (C0921004)

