8. STATISTICAL CALCULATIONS

8.1. Derived and Transformed Data

- Age in years will be calculated as (date minus date of birth)/365.25, rounded down to nearest integer.
- Duration from primary vaccination to any persistence time point will use day of primary vaccination as Day 0. Duration from booster will use day of booster vaccination as Day 0.
- Activity date is defined as the date associated with any activity performed at indicated visit.
- For a given subject and a given immunogenicity measurement, missing or non-evaluable measurements will not be replaced. Therefore, an analysis will exclude subjects with missing or non-evaluable measurements.
- The cutoff values for the assays are defined by the laboratory before the analysis and are described in Section 5.7.3 of the protocol.

MenACWY-TT-100 (C0921004)

- A seronegative subject is a subject whose titer is below the cutoff value.
- A seropositive subject is a subject whose titer is greater than or equal to the cutoff value.
- GMTs are calculated by taking the antilog of the mean of the log titer transformations. Antibody titers below the cutoff value of the assay will be given an arbitrary value of half the cutoff value for the purpose of the GMT calculation.
- rSBA vaccine response for groups A, C, W-135, and Y after the booster dose is defined as:
 - For initially seronegative subjects (pre-vaccination titer <1:8): rSBA antibody titers ≥1:32 1 month after vaccination, and
 - For initially seropositive subjects (pre-vaccination titer ≥1:8): a 4-fold increase in rSBA antibody titers 1 month after vaccination.
- hSBA vaccine response for groups A, C, W-135, and Y after the booster dose is defined as:
 - For initially seronegative subjects (pre-vaccination hSBA titer <1:4): hSBA antibody titers ≥1:8 1 month after vaccination, and
 - For initially seropositive subjects (pre-vaccination hSBA titer ≥1:4): a 4-fold increase in hSBA antibody titers 1 month after vaccination.
- For subjects who received MenC vaccine because they were suboptimal responders during the persistence phase of the MenACWY-TT-027 study, all subsequent persistence results for MenC will be replaced by half the cutoff in order to reflect the immunogenicity of the subjects, had they not been revaccinated. This includes Month 126. However, there will be no adjustment to postbooster MenC titers.

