8.3.1. Methodology for Computing CI

- All CI computed will be two-sided 95% CI.
- The exact 95% CIs for a proportion within a group will be based on the method by Clopper and Pearson [Clopper and Pearson, 1934].
- The standardized asymptotic 95% CI for the group difference in proportions will be based on method 6 described in paper by Newcombe [R Newcombe, 1998].²
- The 95% CI for GMTs will be obtained within each vaccine group separately. The 95% CI for the mean of log-transformed titer will be first obtained assuming that log-transformed values were normally distributed with unknown variance. The 95% CI for the GMTs will be then obtained by exponential transformation of the 95% CI for the mean of log-transformed titer.
- The 95% CIs of the group GMT ratios will be computed using an ANOVA model on the logarithm₁₀ transformation of the titers. The ANOVA model will include the vaccine group as a covariate. Age strata will also be included as a covariate when comparing ACWY>2 to MenPS. In each pairwise comparison, the ANOVA model will use only data from the 2 groups being compared.

MenACWY-TT-100 (C0921004)

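### The visit-wise GMT ratios leave out the pre-vaccination (Month 0) titre that the sponsor already holds, giving up a probably modest amount of precision and any adjustment for baseline differences among attenders

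*SAP*

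**What the plan says.** **Visit-wise ratios.** SAP 7.1.2.2 obtains each GMT ratio from an ANOVA on the log10 "transformation of the titers using the vaccine group as covariate", using only the two groups compared. For ACWY≥2 versus MenPS the model "will also include age strata 2-<6 and 6-<11 years of age at primary vaccination". SAP 8.3.1 repeats this ("Age strata will also be included as a covariate when comparing" those two groups), and Protocol 10.5.1.2.2 describes an ANOVA "using the vaccine group and age stratum as covariates". For ACWY<2 versus MenCCRM, vaccine group is the only term in the SAP. Month 0 titre appears in neither model.

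**What is held.** SAP Table 4 shows Month 0 rSBA for both age groups, all from GSK. SAP Table 5 shows Month 0 hSBA for 1-<2 and 6-<11 years, and none for 2-<6 years.

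**Where Month 0 is used.** The longitudinal analysis in SAP 7.1.3 takes in "Pre- and post-primary analyses (Month 0 and Month 1 in Study MenACWY-TT-027) for subjects belonging in the ATP cohort for immunogenicity", together with the Month 12 to 60 and Month 78 to 126 titres. It fits them all as outcomes with an unstructured covariance and "MODEL log_val = group | time", adding age category in 2-<11 years. Protocol 10.5.1.2.2 says this analysis is meant to reduce bias from loss to follow-up.

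**Status.** The groups come from a randomised study ("613 healthy subjects between 1 and 10 years of age were randomized using a (3:1) ratio", Protocol 1.2). SAP 7.1.2.2 calls the between-group comparisons exploratory, and Protocol 10.6 calls all analyses descriptive.

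**The concern.** Month 0 titre was measured before vaccination, so within an age stratum randomisation gives the two groups the same expected value. Adjusting for it is legitimate, and it narrows the interval to the extent that it predicts the later titre.

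The primary objective is worded as a comparison. The 7.1.2.2 ratios are the only between-group GMT estimates that the SAP spells out, and each control group is expected to fall to 41 subjects by Year 10. Subjects may attend any visit at their own discretion (Protocol 4.1), and investigators receive results and group allocation as the time points are reported (Protocol 5.7.5). Attenders therefore need not keep the randomised balance. An ANOVA restricted to attenders, with no baseline term, passes any Month 0 difference among them into the ratio in proportion to how strongly Month 0 predicts Month X.

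**Working it through.** **1. Attendance at Year 10 (inputs from Protocol 10.3).** 80% of 613 = 490.4; the plan states 488. Then 488 × 0.9⁴ = 320.2; the plan states 326. Multiplying each group by 0.9 per year and rounding up gives 61 → 55 → 50 → 45 → 41 and 183 → 165 → 149 → 135 → 122 (the plan has 150 at Year 8). The total is 2 × 41 + 2 × 122 = 326, the stated figure.

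- All: 326/613 = 53.2%
- MenACWY-TT: 244/460 = 53.0%
- MenCCRM: 41/75 = 54.7%
- MenPS: 41/78 = 52.6%

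So about half are expected, at nearly equal rates in the groups.

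**2. Precision.** The documents state no precision for the GMT ratio, no log10 SD and no correlation ρ between Month 0 and Month X titres within group. All three are therefore assumed over a range. The 95% half-width on the log10 scale is t × SD × √(1−ρ²) × √(1/122 + 1/41), with one degree of freedom lost to the covariate. Apart from that degree of freedom, the width falls by 1 − √(1−ρ²). The last three columns give the factor by which the ratio is multiplied and divided to reach its limits.

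| ρ | CI narrower by | SD 0.6 | SD 0.8 | SD 1.0 |
|---|---|---|---|---|
| 0 (planned) | – | 1.64 | 1.93 | 2.27 |
| 0.1 | 0.5% | 1.63 | 1.93 | 2.27 |
| 0.2 | 2.0% | 1.62 | 1.91 | 2.24 |
| 0.3 | 4.6% | 1.60 | 1.87 | 2.19 |
| 0.4 | 8.3% | 1.57 | 1.83 | 2.13 |
| 0.5 | 13.4% | 1.53 | 1.77 | 2.04 |

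**3. Imbalance among attenders.** If attenders differ between groups by d log10 at Month 0, and the SDs are equal at the two times, the unadjusted ratio is off by a factor 10^(ρd). For d from 0.1 to 0.3 this is 1.02 to 1.07 at ρ = 0.1, 1.07 to 1.23 at ρ = 0.3, and 1.12 to 1.41 at ρ = 0.5. The documents give no value for d.

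**4. What the longitudinal model already does.** A deliberately strong simulation used 230 versus 78 subjects, SD 0.8, one baseline and one later visit, and attendance tied to Month 0 titre in the control group only. Bias in the log10 ratio was:

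| ρ | Planned ANOVA | ANCOVA on Month 0 | Likelihood model, Month 0 as outcome |
|---|---|---|---|
| 0.1 | −0.03 | 0.00 | 0.00 |
| 0.3 | −0.09 | 0.00 | 0.00 |
| 0.5 | −0.16 | 0.00 | 0.00 |

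The last column has the form of the 7.1.3 model reduced to two time points. It removes attendance bias of this kind because it carries the Month 0 titres of non-returners into the later means. It does not adjust for a chance Month 0 difference between the full groups. At ρ = 0.5 the sampling SD of the estimate was 0.144 for the ANOVA, 0.140 for the likelihood model and 0.129 for ANCOVA.

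**5. Age.** If ages are uniform over 2 to 11 years (assumed), age variance is 81/12 = 6.75. The variance left within strata is (4/9)(16/12) + (5/9)(25/12) = 1.75. The strata therefore carry 1 − 1.75/6.75 = 74% of it. Continuous age would narrow the CI by a further 0.1% to 2.4% for an age-titre correlation of 0.1 to 0.4.

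**The case against.** The strongest reply is that the plan already has an analysis for loss to follow-up. The 7.1.3 model uses Month 0, Month 1 and all later titres of ATP subjects whether or not they return, which is more history than a Month 0 covariate would use. This stands. A reader might infer that attendance-related bias is uncorrected throughout, or that letting the groups differ at Month 0 means that later contrasts gain nothing from baseline. The documents support neither inference. The first overlooks 7.1.3, and the second is true only when no later visit is missing. Limits remain, however:

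- the analysis is complementary and done at Month 126;
- the code shows no statement producing a group ratio;
- hSBA in 2-<11 years starts at Month 78;
- the visit-wise ratios stay unadjusted.

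A reader might also infer that age is ignored. It is not: the strata are in the one comparison where age in years varies. In the 1-<2 group, SAP 8.1 ("Age in years will be calculated as (date minus date of birth)/365.25, rounded down to nearest integer") makes age at primary vaccination equal to 1 for everyone.

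Nor does 53% attendance by itself show imbalance. Selection would have to differ by group, and the planned rates are nearly equal, although equal rates do not prove that attenders are alike.

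Finally, ρ over ten years may be low. Month 0 rSBA comes from GSK and the Year 6 to 10 results from PHE, which SAP 7.1.3 describes as about one order of magnitude lower. Values below cutoff are set to half the cutoff, as are MenC persistence results after revaccination. A uniform log shift between laboratories would be absorbed by the intercept and causes no bias, but weaker correlation does reduce the gain.

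**Conclusion.** The point holds in a limited form. The visit-wise GMT ratios omit a valid pre-vaccination covariate already in the sponsor's data, so they forgo some precision and do not adjust for baseline imbalance among attenders. The expected narrowing is about 0.5% to 5% for correlations of 0.1 to 0.3, and 8% to 13% for 0.4 to 0.5. These correlations are assumed, and the low end is plausible, especially in toddlers if most are below cutoff at Month 0. Covariate adjustment removes only the part of any imbalance that Month 0 explains. The comparisons are exploratory and descriptive, with no margin or power attached, so no conclusion of the study turns on this. It is worth making because it costs almost nothing.

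**What to change.** - **SAP 7.1.2.2 and 8.3.1.** For rSBA in both comparisons, and for hSBA-MenC in ACWY<2 versus MenCCRM, add Month 0 log10 titre (same serogroup and assay) as a covariate. Keep the age stratum for ACWY≥2 versus MenPS. Set a missing Month 0 value to the stratum mean, pooled over groups, so that nobody is dropped. Report the currently planned model alongside.
- **hSBA in 2-<11 years.** Leave as planned, because the 2-<6 subjects have no Month 0 hSBA.
- **SAP 7.1.3.** Where Month 0 is in the model, constrain the two randomised groups to one common Month 0 mean. State that the Month 126 group contrast, as a GMT ratio with 95% CI, will be reported from that model.
- **Continuous age.** Optional; it adds little beyond the strata.

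The cost is SAP wording and a few lines of code, with no new data. The small downside is that the adjusted model differs by assay and age group, which table footnotes should state.

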7.1.3. Modeling Prediction

In order to complement the descriptive analyses of observed persistence per time point, longitudinal analyses will be performed at Month 126, which is the last persistence time point before booster vaccination.

Except as noted below, these longitudinal analyses will include all titers from:

- Pre- and post-primary analyses (Month 0 and Month 1 in Study MenACWY-TT-027) for subjects belonging in the ATP cohort for immunogenicity,
- Months 12, 24, 36, 48, and 60 (in Studies MenACWY-TT-028, 029, 030, 031, and 032 respectively) for subjects belonging in the ATP cohort for persistence in corresponding studies and
- Months 78, 90, 102, 114, and 126 (in Study MenACWY-TT-100) for subjects belonging in the ATP cohort for persistence at Month 78 up to Month 126, respectively.

Age group is nearly confounded with vaccine group. Subjects 1-<2 years are assigned only to ACWY<2 and MenCCRM vaccine groups, while subjects 2-<11 years are assigned only to ACWY>2 and MenPS vaccine groups. Therefore the longitudinal analyses will be performed separately in the 2 age strata.

MenACWY-TT-100 (C0921004)

Titers below the cutoff will be set at half the value of the cutoff. The time points will be considered as categorical. The model will be fitted via the proc mixed procedure according to the following code, depending on the age cohort:

```
* for 1-<2 year subjects;

*Model 1 – Repeated model on all available time points;

PROC MIXED data=sero;

CLASS group time;

MODEL log_val = group | time;

Repeated time / TYPE=UN SUBJECT=pid;

RUN;

*for 2-<11 year cohort;
```

PROC MIXED data=sero;

CLASS group time age cat;

MODEL log val = group | time age cat;

Repeated time / TYPE=UN SUBJECT=pid;

RUN;

where 'age cat' will be defined as '2-<6 yr' and '6-<11 yr'.

The exceptions and limitations to the longitudinal analyses are:

- rSBA titers at Year 4 will be limited to PHE titers, even though GSK also obtained some Year 4 titers, because PHE performed all subsequent rSBAs.
- Only MenC titers will be analyzed in the 1-<2 year age group because MenCCRM does not have an A, W-135, or Y component.
- hSBA analyses for the 2-<11 year age group will be limited to Month 78 (Year 6) through Month 126 (Year 10) time points because there are no hSBA titers for 2-<6 year subjects (see Table 5).

MenACWY-TT-100 (C0921004)

Inspection of the observed rSBA geometric means from Month 0 to Year 5 in TT-032 suggests that PHE titers are about 1 order of magnitude lower than GSK titers. In spite of the apparent change in titers all time points will be retained in the modelling prediction. The modeling prediction method specifies that time point is a categorical variable, so the abrupt change starting Year 4 will be captured in the model. Interpretation of the model's predicted values should keep the change in laboratories in mind.

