2. OBJECTIVE(S)

2.1. Primary objectives

Long-term persistence phase: Six, seven, eight, nine and ten years after primary vaccination with MenACWY-TT or *Meningitec* or *Mencevax ACWY*, in study MenACWY-TT-027

- To evaluate the long-term persistence of the serum bactericidal (antibody) titres induced by MenACWY-TT vaccine as compared to *Meningitec* when administered to individuals 1-<2 years of age in terms of the percentage of subjects with *Neisseria meningitidis* serogroup A (MenA), serogroup C (MenC), serogroup W-135 (MenW-135), and serogroup Y (MenY) titres ≥1:8, ≥1:128 and GMTs as measured by a serum bactericidal assay using rabbit complement (rSBA) in those subjects that received MenACWY-TT, and serogroup C (MenC) rSBA titres ≥1:8, ≥1:128 and GMTs in those subjects that received *Meningitec*.
- To evaluate the long-term persistence of the serum bactericidal (antibody) titres induced by MenACWY-TT vaccine as compared to *Mencevax ACWY* when administered to individuals 2-10 years of age in terms of the percentage of subjects with *Neisseria meningitidis* serogroup A (MenA), serogroup C (MenC), serogroup W-135 (MenW-135), and serogroup Y (MenY) titres ≥1:8, ≥1:128 and GMTs as measured by a serum bactericidal assay using rabbit complement (rSBA).

Refer to Section 10.1 for the definition of the primary endpoints.

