10.3. Determination of sample size

The actual sample size of this study with respect to the analysis of persistence and safety and immunogenicity post-booster is determined by a) the sample size of the primary vaccination study MenACWY-TT-027 (108658), b) by assumptions about the enrolment rate at the Year 6-10 extension study, and c) by assumptions about the annual dropout rate. All subjects who were vaccinated in study MenACWY-TT-027 (108658) and received either MenACWY-TT vaccine, *Meningitec* or *Mencevax ACWY* in study MenACWY-TT-027 (108658) will be eligible for this study if they meet the inclusion/exclusion criteria. Six hundred and thirteen subjects (460 in the ACWY-TT group and 75 in the MenCCRM group and 78 in the MenPS group) were enrolled and vaccinated in study MenACWY-TT-027 (108658). An enrollment rate equivalent to approximately 80% of the vaccinated population in study MenACWY-TT-027 (108658) is assumed, and an annual dropout rate of 10%.

If one assumes approximately 10% of subjects dropping out of the persistence study at every visit, then one expects the following numbers of subjects to participate at each persistence time point.

- For the analysis at Year 6, it is estimated that approximately 488 subjects will be enrolled (183 in the ACWY<2, 183 in the ACWY≥2 group, 61 in the MenCCRM group and 61 in the MenPS group)
- For the analysis at Year 7, it is estimated that approximately 440 subjects will be enrolled (165 in the ACWY<2, 165 in the ACWY≥2 group, 55 in the MenCCRM group and 55 in the MenPS group)

C0921004 (MenACWY-TT-100 EXT:027 Y6,7,8,9,10, 200171)
Protocol Amendment 2

- For the analysis at Year 8, it is estimated that approximately 400 subjects will be enrolled (150 in the ACWY<2, 150 in the ACWY≥2 group, 50 in the MenCCRM group and 50 in the MenPS group)
- For the analysis at Year 9, it is estimated that approximately 360 subjects will be enrolled (135 in the ACWY<2, 135 in the ACWY≥2 group, 45 in the MenCCRM group and 45 in the MenPS group)
- For the analysis at Year 10, it is estimated that approximately 326 subjects will be enrolled (122 in the ACWY<2, 122 in the ACWY≥2 group, 41 in the MenCCRM group and 41 in the MenPS group)

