7.1.2. Analysis of Persistence

The persistence analyses will be based on the adapted ATP cohort. If for any vaccine group, at any time point, the percentage of subjects who have serological results but are otherwise excluded for the corresponding ATP cohort is higher than 10%, a second analysis based on the total enrolled cohort will be performed to complement the ATP analysis. The percentage of subjects with excluded serological results will compiled separately for the MenC ATP persistence cohort and the MenAWY ATP persistence cohort.

Different laboratories performed the rSBAs and hSBAs at different time points. rSBAs were performed either by GSK or Public Health England (PHE) (see Table 4). hSBAs were performed either by GSK or Neomed (Neomed was a GSK facility until it was spun off as an independent company) (see Table 5). Furthermore, GSK did not perform hSBAs for 2-<6 year subjects. The consequences will be described in Section 7.1.2.1, Section 7.1.2.2, and Section 7.1.3.

Table 4. Description of Laboratories Performing rSBAs by Time Point

		GSK		PHE	
Study MenACWY-	Time Point	1-<2 years	2-<11 years	1-<2 years	2-<11 years
TT-027	Baseline (Month 0)	✓	√		
	Month 1	✓	√		
TT-028	Year 1	✓	✓		
TT-029	Year 2	✓	✓		
TT-030	Year 3	✓	✓		
TT-031	Year 4	✓	✓	√	✓
TT-032	Year 5			✓	✓
TT-100	Month 78 (Year 6)			√	✓
	Month 90 (Year 7)			√	✓
	Month 102 (Year 8)			✓	✓
	Month 114 (Year 9)			✓	✓
	Month 126 (Year 10)			√	✓
	Month 127			√	√

Abbreviations: rSBA = serum bactericidal assay against *Neisseria meningitidis* using rabbit complement.

MenACWY-TT-100 (C0921004)

Table 5. Description of Laboratories Performing hSBAs by Time Point

		GS	GSK		Neomed	
Study MenACWY-	Time Point	1-<2 years	6-<11 years	1-<2 years	2-<11 years	
TT-027	Baseline (Month 0)	✓	✓			
	Month 1	✓	✓			
TT-028	Year 1	✓	√			
TT-029	Year 2	✓				
TT-030	Year 3	✓				
TT-031	Year 4	✓				
TT-032	Year 5	✓				
TT-100	Month 78 (Year 6)			√	√	
	Month 90 (Year 7)			√	√	
	Month 102 (Year 8)			✓	√	
	Month 114 (Year 9)			√	√	
	Month 126 (Year 10)			√	√	
	Month 127			✓	√	

Abbreviations: hSBA = serum bactericidal assay against Neisseria meningitidis using human complement.

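### In children vaccinated at 1-<2 years, the SAP runs the longitudinal model for MenC only, so the protocol's planned check on loss to follow-up is missing for MenA, MenW-135 and MenY, and SAP Section 10 does not record the change.

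*SAP*

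**What the plan says.** Protocol 10.5.1.2.2, under its modelling paragraph, gives two aims: to complement the results at each time point, and to "minimize the bias that may have occurred due to the loss to follow-up after the vaccination, a longitudinal analysis will be performed". The scope is "for rSBA-MenA, C, W-135 and Y and/or hSBA-MenA, C, W-135 and Y". No age group or study group is excepted, and further detail is left to the SAP.

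SAP 7.1.3 opens with only the first aim: "In order to complement the descriptive analyses of observed persistence per time point, longitudinal analyses will be performed at Month 126". It fits the two age strata separately and lists this exception: "Only MenC titers will be analyzed in the 1-<2 year age group because MenCCRM does not have an A, W-135, or Y component". SAP Section 10, on changes from planned analyses, covers the cohorts and the handling of MenC-revaccinated children. It does not mention the longitudinal model.

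Protocol 2.1 places all four serogroups in the primary objective for the younger children, "as measured by a serum bactericidal assay using rabbit complement (rSBA) in those subjects that received MenACWY-TT". SAP 7.1.2.1 still tabulates observed GMTs, percentages and distribution curves for each serogroup and visit.

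**The concern.** The absence of A, W-135 and Y from MenCCRM means there is no meaningful comparator for those serogroups. It does not remove the ACWY<2 titres: SAP Table 4 shows rSBA testing at 1-<2 years at every time point. A mean over time in one group needs no comparator.

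Without the model, these three serogroups have only available-case summaries, because under SAP 8.1 "an analysis will exclude subjects with missing or non-evaluable measurements". The second analysis in SAP 7.1.2 does not fill the gap. It is triggered when "the percentage of subjects who have serological results but are otherwise excluded for the corresponding ATP cohort is higher than 10" per cent, so it concerns children who gave blood and were then excluded, not children who stayed away. Protocol 4.1 lets families choose visit by visit whether to attend.

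If children with lower earlier titres attend less often, the observed GMTs will be too high, increasingly so as attendance falls, and nothing planned for these serogroups would show it. W-135 and Y had the lowest detectable percentages in this age group at Year 5 (34.7% and 42.9%, protocol 1.2). Monovalent MenC revaccination is not the issue, since it does not remove a child from the MenAWY cohort. The issue is non-attendance.

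**Working it through.** **1. Scope.** Per assay, the protocol names 4 serogroups. In the 1-<2 year stratum the SAP models 1 (MenC), so 3 of 4 are not run. The protocol's and/or leaves the choice of assay open, not the choice of serogroups.

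**2. Attrition (protocol 10.3).** The plan assumes 80% enrolment and 10% annual dropout, and at Year 10 expects "approximately 326 subjects will be enrolled (122 in the ACWY<2" group).

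- Enrolment: 0.80 × 613 = 490.4 (stated 488).
- ACWY<2, each year from the previous stated figure: 183 × 0.9 = 164.7; 165 × 0.9 = 148.5; 150 × 0.9 = 135.0; 135 × 0.9 = 121.5. Stated: 165, 150, 135, 122. The plan's figures are reproduced to within 2.
- Remaining in ACWY<2, Year 6 to Year 10: 122/183 = 66.7%. Remaining overall from primary vaccination: 326/613 = 53.2%.

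**3. Simulated size of the bias (hypothetical).**

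- From the documents: attendance 183/165/150/135/122; 34.7% or 42.9% detectable, held constant; titres below 1:8 set to half the cut-off, log10(4).
- Assumed: normal underlying log10 titres; between-visit correlation 0.75; underlying SD 0.6-0.8, or SD 0.8 after flooring; permanent or intermittent absence; attendance odds falling 1.65-fold or 2.7-fold per 10-fold lower titre.
- Method: 250-300 replicates per scenario. The Month 126 observed GMT and the GMT from an unstructured multivariate-normal model (maximum likelihood by EM) are each divided by the GMT of all 183.

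| Attendance depends on | log10 SD | Odds ratio | Observed / full | Model / full |
|---|---|---|---|---|
| last observed titre | underlying 0.6-0.8 | 1.65 | 1.032-1.080 | 0.996-1.003 |
| last observed titre | underlying 0.6-0.8 | 2.7 | 1.065-1.139 | 0.996-1.003 |
| last observed titre | 0.8 after flooring | 1.65 | 1.151-1.166 | 0.996-1.003 |
| last observed titre | 0.8 after flooring | 2.7 | 1.234-1.279 | 0.996-1.003 |
| current titre | underlying 0.6-0.8 | range run | 1.046-1.200 | 1.015-1.073 |
| current titre | 0.8 after flooring | range run | 1.182-1.416 | 1.045-1.144 |
| neither | range run | 1 | 0.994-1.009 | not needed |

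The model column for the last-observed-titre rows is one range across all of them.

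**4. Reading these ratios.** One third of the group is absent (61/183), so observed/full = (attending GMT / absent GMT)^(1/3). A ratio of 1.03 means 1.03³ = 1.09: attenders' GMT is 1.09 times that of absentees. A ratio of 1.08 means 1.08³ = 1.26, and 1.28 means 1.28³ = 2.10.

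**5. Threshold percentages.** In the last-observed-titre scenarios the available-case percentage ≥1:8 is 1.4-5.7 points too high. As a direct check, if absentees' true rate is 10 to 20 points below attenders', the excess is 61/183 × 10 = 3.3 to 61/183 × 20 = 6.7 points. The proposed model works on log titres and does not change these percentages.

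**6. Feasibility.** All time points: 12 visits, 12 × 13/2 = 78 covariance parameters. PHE series from Year 4 to Month 126: 7 visits, 7 × 8/2 = 28. A check with 12 visits, a 1 log10 laboratory shift at Year 4 and assumed earlier attendance of 75-100% (40 replicates, 34.7% detectable, underlying SD 0.8) gave 1.004 for both the 12-visit and 7-visit fits, without numerical failure. The observed ratios were 1.061 (odds ratio 1.65) and 1.103 (2.7).

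**The case against.** **It is specification, not a change.** The modelling paragraph sits under a between-group heading where the only ACWY<2 contrast is MenC, and details were left to the SAP. This has some force, but the protocol sentence names four serogroups, and its aim concerns observed persistence at each time point, which is a within-group quantity. The heading does not narrow that.

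**Nothing is hidden.** SAP 7.1.3 states the limit and its reason. Section 10 leaves changes for the study report to its review, and protocol 10.7 requires deviations to be justified in the final report. This is correct, so the recording gap alone is small.

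**The primary results are intact.** All analyses are descriptive, the model is a complement, and it would not adjust the ≥1:8 and ≥1:128 percentages, which are two of the three primary measures. This stands and limits the weight of the point.

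**The harm is conditional.** No passage shows that attendance depends on titre, and the correlation, SDs and odds ratios are assumed. At N = 122 the 95% interval for the GMT spans a factor of about 1.17-1.25 either way (underlying SD 0.6-0.8) or 1.39 (SD 0.8 after flooring), so the last-observed-titre biases lie inside it. That also stands. However, such a bias has one direction and can grow as attendance falls, so it could mask waning, and the interval does not allow for it.

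**The model has limits.** At Year 5, 65.3% (W-135) and 57.1% (Y) were below detection, the laboratory changed, and a mixed model handles only dropout explained by observed titres. The simulations include the flooring, and one check includes the laboratory shift. The last limit is real: when attendance follows the current titre, 2-14% bias remains.

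**Conclusion.** The concern holds. The mismatch between protocol and SAP is certain from the text, and the SAP's reason supports dropping a group contrast, not the within-group estimate. The size of any bias is unknown. Under the stated assumptions, the Month 126 GMT would be overstated by 3-8% or 15-17% at an odds ratio of 1.65, and by 7-14% or 23-28% at 2.7 (first range for underlying SD 0.6-0.8, second for SD 0.8 after flooring). It would be within 1% if attendance does not depend on titre. Selection before Month 78 was not simulated, and the fits used EM rather than PROC MIXED.

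The SAP already accepts that selection can distort persistence: Section 10 keeps MenC-revaccinated children because leaving them out would inflate MenC persistence. The change should be made, but it does not threaten the trial's validity.

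**What to change.** In SAP 7.1.3, add a model for rSBA-MenA, MenW-135 and MenY in ACWY<2 alone (hSBA optional, given the protocol's wording):

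`CLASS time; MODEL log_val = time; REPEATED time / TYPE=UN SUBJECT=pid;`

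- Use the same time points as the MenC model, and state a fallback if it does not converge, for example the PHE series from Year 4 to Month 126.
- Report the Month 78-126 least-squares GMTs with 95% CIs beside the observed GMTs.
- State that the model corrects only for dropout explained by observed titres and does not adjust the threshold percentages.
- Restore the loss-to-follow-up aim in 7.1.3 and record the change in Section 10. If the sponsor keeps the MenC-only limit, Section 10 should at least record and justify it.

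The cost is SAP wording and a few extra model runs on data already held. No visit, sample or error rate is affected.
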